4.9 Study Limitations

This study is subject to several potential limitations. First, losses to follow-up may reduce our effective sample size, thus diminishing our power to detect significance in some variables. However, our prior work in this area suggests that our losses to follow-up will be less than 5%. Furthermore, our study sample size has compensated for these potential losses to follow-up and we thus do not anticipate this to be an issue. Second, heterogeneity in outcomes may impact modelling of post-discharge events. We observed this to be a potential limitation in our prior work, in that the predictors were different between newborns and mothers, and even among mothers, between those with caesarean sections and those who delivered vaginally. To improve our probability of success, therefore, our sample size was developed to be able to model at least 3 separate outcomes. We anticipate that this will be sufficient to create a set of models which are comprehensive to capture various outcomes. Finally, With limited numbers of focus group discussions, this study may not reach thematic saturation. If this is deemed to be the case we will add additional focus groups, following a protocol amendment.

4.10 Data Analysis

Data will be spot checked by a core study staff member for quality verification and will be cleaned and coded by a research assistant. Data will be cleaned, coded, and analyzed using R Statistical Software for quantitative data and NVivo Software for qualitative data. Coded qualitative data from transcriptions and written narratives will be reviewed during team meetings and consensus will be reached on any discrepancies.

Quantitative Analysis: We will summarise all risk factors for mothers and newborns that do and do not experience poor outcomes and estimate univariate associations. For newborns, data will be reported by sex. Derivation of prediction models will be based on optimization of the area under the receiver operating curve (AUROC) and specificity across a variety of modeling and variable selection approaches (e.g., logistic regression, elastic net, support vector machines). Model performance will be based on appropriate resampling techniques for internal validation (e.g., cross-validation, bootstrapping). We will focus on developing parsimonious predictive models (e.g., 5-10 predictor variables) with high sensitivity (>80%). AUROC, sensitivity, and specificity will be reported for each model, along with positive and negative predictive values. Site specific metrics will be compared to ensure consistency across settings, and recalibration may be considered if individual site performance is lower than expected. Finally, we will assess combined sensitivity and specificity when each individual model is applied to the dyad. Outside of prediction modelling, our sample size will allow us to detect an odds ratio of at least 1.30 for a given risk factor with 80% power and 5% significance and relative precision of 25%. Statistical analysis of quantitative data from journey mapping observation surveys and patient interviews will be performed using R Statistical software to obtain descriptive statistics of the frequency and distribution of each variable.

Qualitative Analysis: We will analyze data collected descriptively and report summary statistics. We will develop a diagram of the discharge process, identifying key areas for improvement during the peri-discharge and post-discharge process¹¹. We will analyze FGDs using a framework method, which allows themes to be developed inductively from participants and deductively from existing literature¹². Through an iterative process, transcripts will be coded and analyzed for descriptive and interpretive themes using NVivo. Descriptive themes include barriers to care and post-discharge health-seeking behavior, while interpretive themes focus on caregiver perspectives of maternal and neonatal death and the role of the health system. We will generate frequencies to describe reported medical symptoms, health-seeking behavior, and barriers to care, and summarize common themes. We will use member checking to improve the validity of our results, creating a summary document of the main findings that will be reviewed by health workers who participated in the focus groups. Feedback from patients and families will be obtained over telephone with research nurses who will explain the main findings verbally.

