2.0 CHAPTER TWO: Problem statement, justification, and conceptual framework

2.1 Problem statement

Neonatal outcomes are highly correlated with the health of the mother, an example of this is shown repeatedly by poor rates of survival of infants after maternal death^{1,2}. Prediction of risk, based on the mother and infant as a pair, is a major gap in current research and yet vital to the survival of both the mom and the infant. In our prior epidemiological study of post-discharge outcomes among 3,236 dyads, we found that most readmissions were due to infectious illness and occurred early in the post-discharge period. Of the 2,926 dyads with complete follow-up data 7.1% of dyads reported at least 1 outcome. 3.6% of newborns were readmitted, 0.8% died, and 2.7% of mothers were readmitted. For readmitted newborns, the most common diagnosis was sepsis (63%), and 19% were in respiratory distress at readmission. For readmitted mothers, the most common diagnoses were surgical site infections (51%), puerperal sepsis (43%), malaria (19%), and other infections (5%). Considering the health of the mother and newborn as a dyad is an innovative and effective approach as the health of a child is closely linked to the health of its mother. A mother's morbidity or mortality affects the health of all her children – and newborns whose mothers died during the first 6 weeks have an even greater risk of dying than those whose mothers survive¹⁵. Thus, we can improve maternal and child health outcomes by identifying both mothers and babies at increased risk of mortality or serious morbidity after hospital discharge and allocating scarce resources for targeted follow-up to those most vulnerable. This allows us to not only improve health outcomes but benefits the health system with efficient use of resources.

[figure not shown]

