4.3 Study Sites

Study activities will be conducted at two hospitals (Mbarara Regional Referral Hospital (MRRH) and Jinja Regional Referral Hospital (JRRH)) in Uganda in the districts of Mbarara and Jinja.

Table 2: Characteristics of the proposed study sites.

District (Region)	Hospital	Type	Location	District population	Annual deliveries
Mbarara (Western)	Mbarara Regional Referral Hospital	Public	Semi-rural	490,000	7,500
Jinja (Eastern)	Jinja Regional Referral Hospital	Public	Urban	483,000	6,000

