4.4 Study Population

Phase I: Observational Cohort Study

We will recruit 7,000 mother and newborn dyads from the two participating hospitals. Based on previously observed outcome and loss to follow-up rates, we will be able to measure the prevalence of maternal and newborn hospital readmission or death within a margin of error of 1% and develop prediction models with up to 30 candidate predictors for both maternal and newborn outcomes separately with this sample size.

Inclusion:

- Women and adolescent girls aged 12 and above delivering a single or multiple babies at the study hospital during the active recruitment phase.

Exclusion:

- Inability, for whatever reason, to provide informed consent.
- Language barrier
- Mother is from a refugee camp
- Mother has no access to phone or other means for follow-up
- Mother lives outside of hospital catchment area

We will continue to follow-up with all patients enrolled in the study. This includes enrolled mothers whose baby dies after discharge as well as enrolled babies whose mothers die. In the event that the mother dies, we will follow-up with the caregiver of the baby.

Table 3. Phase I sample size

Participants:	Sample size (n=7,000)
Maternal Infant Dyads	3,500 per facility (n=7,000)

Phase II: Patient Journey Mapping

We will randomly select 100 mothers (50 per facility) from the phase I cohort of 7,000 dyads to participate in journey mapping due to intense time to capture.

Inclusion:

- Women and adolescent girls aged 12 and above delivering a single or multiple babies at the study hospital during the active recruitment phase.
- Enrolled in Phase 1.

Exclusion:

- Inability, for whatever reason, to provide informed consent.

Exclusion:

- Inability, for whatever reason, to provide informed consent.
- Language barrier
- Mother is from a refugee camp
- Mother has no access to phone or other means for follow-up
- Mother lives outside of hospital catchment area

Table 4. Phase II sample size

Participants:	Sample size (n=100)
Maternal Infant Dyads	50 per facility (n=100)

Phase III: Process Mapping

We will purposively select a sample of 6 healthcare providers and 2 hospital administrators from each of the 2 study sites for participation in a process mapping exercise based on their level of experience, availability, and consultations from site leads (Table 4).

Inclusion:

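### Section 4.10 plans univariate risk-factor associations with no hospital term, although the cohort is drawn equally from two distinct hospitals; a hospital-stratified estimate should be reported beside the crude one

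*Combined protocol and SAP*

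**What the plan says.** The quantitative part of Section 4.10 (Data Analysis) of the combined protocol and SAP opens with this step: "We will summarise all risk factors for mothers and newborns that do and do not experience poor outcomes and estimate univariate associations". After describing the prediction models, it adds a separate statement for risk factors outside that modelling: "our sample size will allow us to detect an odds ratio of at least 1.30 for a given risk factor with 80% power", at 5% significance and a relative precision of 25%.

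On the source of the data, Section 4.3 states: "Study activities will be conducted at two hospitals". Section 4.1 calls them distinct settings, and Table 2 places them in different regions, one semi-rural and one urban. Section 4.4 gives the size: "We will recruit 7,000 mother and newborn dyads from the two participating hospitals". Table 3 splits this equally, 3,500 per hospital.

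Hospital enters Section 4.10 in one place only: prediction performance is to be compared by site, with recalibration considered if a site does worse than expected. Nothing similar is said for the risk-factor associations. The text does not state that they are pooled over hospitals, but with one sample size and no site term that is the natural reading.

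**The concern.** A pooled univariate odds ratio combines two things: the association within each hospital, and any tendency for the hospital with more exposed women to have more (or fewer) outcomes for other reasons. The second part appears only if outcome risk and exposure frequency both differ between hospitals. Several items in Appendix A plausibly differ between an urban and a semi-rural setting: referral, travel time, transport, residence, education, socioeconomic items, and ward practices such as antibiotic use and induction.

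At stake is how the reported risk factors are read. A factor that is unrelated to outcome at either hospital can pass a 5% test, and a real one can be diluted below detection. Because the plan gives these factors a significance level and a power, readers will treat the odds ratios as inferential results about the factor, not only as a table of characteristics.

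**Working it through.** **Inputs from the documents.** 7,000 dyads, 3,500 per hospital (4.4, Table 3). Loss to follow-up expected below 5% (4.9); taking 5% leaves 6,650, or 3,325 per hospital. Dyad outcome rate 7.1% in the prior study (2.1).

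**Assumed, because the documents give nothing.** Outcome risk by hospital (spread around 7.1%), factor frequency by hospital, and a two-sided test.

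**Step 1. The plan's own figure.** With 50% exposed and an overall risk of 7.1%, an odds ratio of 1.30 means risks p0 = 6.24% and p1 = 7.96%. With n per exposure group and p̄ = 0.071,

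power = Φ{[(p1 − p0)√n − 1.96√(2p̄(1 − p̄))] / √(p0(1 − p0) + p1(1 − p1))}.

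For n = 3,500 this is Φ[(1.019 − 0.712)/0.363] = Φ(0.846) = 80.1%. For 6,650 dyads it is 78.1%. The stated 1.30 is therefore reproduced by a crude calculation on the dyad composite, with no hospital term, a factor present in half the cohort, and no loss to follow-up.

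**Step 2. A factor with no effect within either hospital.** Build the expected 2×2 table in each hospital (3,325 dyads, within-hospital odds ratio 1), add the two, and compute

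- crude OR = ad/(bc); SE(ln OR) = √(1/a + 1/b + 1/c + 1/d); z = ln OR/SE;
- rejection probability = Φ(z − 1.96) + Φ(−z − 1.96).

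Risks 5.7% v 8.5%, exposure 40% v 60%:
- exposed with outcome a = 1,330 × 0.057 + 1,995 × 0.085 = 75.8 + 169.6 = 245.4; exposed without, b = 3,079.6
- unexposed with outcome c = 1,995 × 0.057 + 1,330 × 0.085 = 113.7 + 113.1 = 226.8; unexposed without, d = 3,098.2
- OR = (245.4 × 3,098.2)/(3,079.6 × 226.8) = 1.09; z = 0.0849/0.0956 = 0.89; rejection 14%.

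Same risks, exposure 20% v 50%:
- a = 179.2, b = 2,148.3, c = 292.9, d = 4,029.6
- OR = 1.15; z = 0.1376/0.0985 = 1.40; rejection 29%.

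Small differences (6.4% v 7.8%; 30% v 40%): OR = 1.02, rejection 5.6%.

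The hospital-stratified odds ratio is 1.00 in all three.

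**Step 3. Masking.** Now let the true within-hospital odds ratio be 1.30, with the hospital at 20% exposure having the higher risk (8.5%) and the hospital at 50% exposure the lower (5.7%). The pooled table is 174.5, 2,153.0, 297.6, 4,024.9, so the crude OR is 1.10 with z = 0.0917/0.0990 = 0.93 and power 15%. The stratified estimate is 1.30 with SE 0.105, z = 0.2624/0.105 = 2.50 and power about 70%.

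**Step 4. What stratifying costs.** The stratified variance of ln OR is 1/(1/v₁ + 1/v₂), where v₁ and v₂ are the within-hospital variances. Set against the crude variance:

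| Exposure by hospital | Increase in ln OR variance |
|---|---|
| 30% / 40% | about 1% |
| 40% / 60% | about 4% |
| 20% / 50% | 10–13% |
| 15% / 55% | 19–25% |

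The ranges reflect different assumed risks. For a true odds ratio of 1.30 with 6,650 dyads and equal 7.1% risks, stratified power is 77.9% at 50%/50%, 76.3% at 40%/60% and 70.8% at 30%/70%.

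**The case against.** The strongest defence is that this step is descriptive. The hypothesis and Aim 1 concern prediction, and site performance is checked there. A univariate association is a marginal quantity, and for the marginal null the 5% level does hold. It fails only if the reader wants the within-hospital association, which the plan never names. After adjustment for hospital the odds ratios remain unadjusted for everything else. The part that stands is that no causal or adjusted claim is made, and that hospital is one confounder among many. It does not dispose of the point, because the plan itself goes beyond description by stating a significance level and power for these factors outside prediction modelling. Hospital is also a known design stratum with fixed equal quotas.

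The illustrations use the 7.1% dyad composite. For the separate outcomes, at 20% v 50% exposure, rejection is lower: about 20% for newborns (risks 3.5% v 5.3%) and 16% for mothers (2.1% v 3.3%). Both still exceed 5%.

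Three stronger readings are tempting, and the documents do not support them:

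- A reader might infer that hospital differences alone would produce an odds ratio near 1.30. That needs large gaps on both sides: risks of 5.0% v 9.2% with exposure 15% v 55% give 1.31. With a risk ratio of 1.5 the exposure gap must reach 61 points, and with a ratio of 1.2 the value cannot be reached (maximum 1.22). No hospital-level figure in the documents points to such gaps.
- A reader might infer that stratifying is free. Step 4 shows that it is not, and the cost is highest for the factors whose frequency differs most by hospital.
- A reader might infer that these odds ratios decide whom the care bundle targets. Section 4.7 assigns identification of high-risk dyads to the prediction models and draws the bundle from Phases II–IV.

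**Conclusion.** The point holds as a gap in the analysis plan with a better method readily available. It does not show that the results will be wrong. Moderate hospital differences, as assumed above, raise the chance of declaring a null factor significant from 5% to between 14% and 29%, and can cut power for a true odds ratio of 1.30 from about 70% to 15%. Small differences leave the crude analysis practically unaffected. Which case applies cannot be known from the documents; all hospital-specific risks and exposures here are assumptions. The conclusion also rests on reading the planned associations as pooled and on taking the within-hospital association as the quantity of interest. Adjustment for hospital removes between-hospital confounding only.

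**What to change.** In Section 4.10, replace the univariate step with wording such as: *the association of each risk factor with each outcome will be estimated stratified by or adjusted for hospital (logistic regression with a hospital term, or Mantel-Haenszel), with 95% confidence intervals; crude and hospital-specific estimates will be shown alongside.*

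Qualify the power sentence so that the odds ratio of 1.30 applies to factors of similar frequency at both hospitals, and say that power is lower for factors whose frequency depends on the hospital.

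The change needs two amended sentences and one model term. It needs no extra participants or data, since the hospital is known for every dyad. The price is the precision loss in Step 4: about 1% of variance where frequencies are close, rising to about 20% or more at 15% v 55%.

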Currently, the World Health Organization (WHO) recommends three in-person postnatal visits for all mothers and newborn infants born at a health facility within the first six weeks of life⁶. The evidence used in formulating this recommendation is primarily based on timing of maternal and neonatal deaths and evidence surrounding the efficacy of the components of care recommended during the postnatal period. Despite this WHO recommendation, achieving any postpartum follow-up care has been challenging in many low-resourced settings. For example, in Uganda, only 57% of women received one visit with a skilled health care provider within 41 days of delivery³. There is an important opportunity to tailor recommendations for timing and frequency of follow-up to individual risk, to guide the use of scarce healthcare resources. Personalized risk scores can help frontline healthcare providers identify high-risk dyads before discharge from hospital, and guide recommendations for essential PNC. This approach facilitates safer hospital to home transitions and efficient allocation of scarce resources. Adherence to the recommended PNC visits is critical for those at higher risk.

The development of an evidence base upon which to build recommendations for the timing and intensity of postnatal care in resource-poor countries is urgently needed. This study aims to address this gap in care coverage using a precision medicine approach to postpartum follow-up. Our approach to risk stratification integrates data about the health of both the mother and newborn. This ensures that when one is sick, the other can be more closely monitored to prevent their potential decline in health. We are working to expand our innovative precision public health approach to improving post-discharge care for mother-newborn dyads. Our aim is to build a discharge risk prediction score that identifies high-risk dyads before hospital discharge. To achieve this, we will conduct an observational cohort study in 7,000 dyads discharged together after live births at JRRH and MRRH. With the data collected from this study, we will be able to develop prediction models with up to 30 candidate predictors for both maternal and newborn outcomes separately.

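### Recalibration is the named remedy for a weak site, but no calibration measure is planned and the trigger can point to the wrong site

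*Combined protocol and SAP*

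**What the plan says.** All the relevant text is in the quantitative part of section 4.10 (Data Analysis).

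- Model derivation rests on "optimization of the area under the receiver operating curve (AUROC) and specificity across a variety of modeling and variable selection approaches". Logistic regression, elastic net and support vector machines are given as examples. The aim is a model of 5 to 10 predictors with sensitivity above 80%.
- Reporting: "AUROC, sensitivity, and specificity will be reported for each model, along with positive and negative predictive values". Validation is by resampling. At dyad level, combined sensitivity and specificity are added.
- Sites: "Site specific metrics will be compared to ensure consistency across settings", and then "recalibration may be considered if individual site performance is lower than expected".

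The word recalibration is the only reference to calibration in the supplied text. There is no observed/expected ratio (O/E), calibration intercept, slope or plot.

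On use, sections 3.2 and 4.7 describe models that identify high-risk dyads, and section 2.2 describes two tiers of care. Section 1.0 also sees an opportunity to "tailor recommendations for timing and frequency of follow-up to individual risk", and section 2.3 wants the intensity of care tied to how large the risk is. Section 4.4 foresees "prediction models with up to 30 candidate predictors for both maternal and newborn outcomes separately".

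**The concern.** Recalibration corrects predicted risks that are too high, too low or too extreme. Deciding that it is needed, where and in which direction, requires a comparison of predicted with observed risk. The plan contains none. It relies on site performance being low on measures of ranking and classification.

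Two things are at stake. First, the site step may leave a miscalibrated site alone or send recalibration to a site that is already calibrated. Second, a pair of models could be called internally validated without any report on whether the risks are right in size. That matters if the later programme grades follow-up by individual risk. It matters much less if the score is used only as a high/low split.

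**Working it through.** The plan states no figure on this point, so there is none to reproduce. Steps 1 and 2 need no numbers from the trial. Steps 4 to 7 rest on assumed site differences.

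**1. Ranking.** Assume that the cut-off is the one that meets the 80% sensitivity target (my reading; the plan does not say how it is set). If every predicted risk is passed through the same strictly increasing function and the cut-off is set again, the same dyads lie above it. AUROC, sensitivity, specificity, PPV and NPV are then unchanged, whatever happens to the size of the risks.

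**2. Site AUROC.** Recalibration replaces the linear predictor L by a + bL. With b > 0 the order within the site is unchanged, so its AUROC is unchanged. A low site AUROC cannot be repaired this way. It can also occur with nothing to repair: narrowing the spread of the linear predictor from SD 1 to 0.6 in a calibrated model lowers AUROC from 0.756 to 0.663 at 2.7% risk, with O/E still 1.00.

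**3. Inputs.** Section 2.1 gives a maternal readmission risk of 2.7% and newborn risks of 3.6% (readmission) and 0.8% (death), so 4.4% if they do not overlap. Table 3 in section 4.4 gives 3,500 dyads per site. Section 4.9 expects losses under 5%; at 5%, 3,500 × 0.95 = 3,325 remain per site. Events per site are 3,325 × 0.027 ≈ 90 (maternal) and 3,325 × 0.044 ≈ 146 (newborn). Assumptions: linear predictor SD 1, AUROC about 0.75, equal sites, one pooled logistic model without a site term, one common cut-off at 80% pooled sensitivity. Paired figures below are maternal / newborn.

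**4. Baseline risk differs twofold in odds, not captured by the predictors.**

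| Measure | Lower-risk site | Higher-risk site |
|---|---|---|
| O/E | about 0.69 | about 1.31 |
| PPV | 3.3% / 5.3% | 6.3% / 9.9% |
| NPV | 99.4% / 98.9% | 98.7% / 97.8% |

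AUROC, sensitivity and specificity differ by about 0.01. PPV is lower at the over-predicted site and NPV at the under-predicted one, so which site counts as low depends on the metric. Over a range of shifts, O/E is about 0.82 against 1.18 at 1.5-fold and 0.52 against 1.48 at threefold.

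**5. Case mix differs by the same amount, model calibrated at both sites.** O/E is 1.00 at both. Sensitivity is 0.67 against 0.87, specificity 0.71 against 0.44, PPV 4.1% against 5.4% / 6.7% against 8.7%. In simulated studies the sensitivity gap is significant in 87% / 97%. The O/E interval flags a site in about 1% or fewer.

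**6. A case where the rule works.** If predictors are recorded lower by ln 2 at one site, sensitivity there falls to 0.70 with O/E 1.38, and the rule points to the right site.

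**7. Detection.** At twofold odds, a site-to-site PPV test finds the difference in 97.1% / 99.7% of studies, and a site O/E interval excluding 1 does so in 94% / 99.5%. At 1.5-fold the figures are 64% / 82% for PPV and 39% / 64% for the O/E interval. The O/E rule loses because each site is compared with a pooled average that includes it. With no site difference it flags only 0.3% to 0.6% of studies.

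A direct comparison of the two sites recovers the loss. At 1.5-fold:
- Observed events are 90 × 0.82 = 74 and 90 × 1.18 = 106 (maternal), and 146 × 0.82 = 120 and 146 × 1.18 = 172 (newborn).
- The log ratio is ln(1.18/0.82) = 0.364.
- The standard errors are √(1/74 + 1/106) = 0.151 and √(1/120 + 1/172) = 0.119.
- z = 2.40 / 3.06, so the approximate detection is 67% / 86%, about the same as PPV.

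**8. Precision.** The 95% limits for a site O/E near 1 are exp(±1.96/√90) = 0.81 to 1.23 and exp(±1.96/√146) = 0.85 to 1.18.

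**9. Overfitting.** 2 × 3,325 = 6,650 dyads give 6,650 × 0.027 ≈ 180 and 6,650 × 0.044 ≈ 293 events, so 180/30 = 6 and 293/30 ≈ 10 per candidate predictor. After the 10 strongest of 30 simulated predictors were picked, the mean calibration slope in new data was 0.82–0.92 / 0.86–0.95. Elastic net, which shrinks coefficients, was not simulated.

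**The case against.** The strongest objection is that the declared product is a classification. For a cut-off chosen by sensitivity, the five metrics are the relevant ones, and PPV and 1 − NPV already give the observed risk in each tier. Care in two tiers can also be read as intensity linked to risk. This stands: the high/low split is served, and the case for correct absolute risks rests on sections 1.0 and 2.3, which state aims and not a specified numerical use.

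Second, the site differences in the working are hypothetical. The documents give no site-specific event rates. Residence variables or a site term could absorb a baseline difference, and if recalibration is meant to include re-estimating coefficients, AUROC can change. This also stands, and it limits the site argument to what can happen.

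Third, the step is optional, and an analyst could compare observed with predicted events before acting. That is true, but the plan does not ask for it and gives no criterion.

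Fourth, the planned PPV comparison detects a site difference at least as often as a site O/E interval does. That is correct. However, PPV also moves with case mix (step 5), so it shows that sites differ without showing whether the predictions are wrong.

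A reader might go further and infer that the pooled risks will be wrong by a large factor, or that the models will misclassify dyads. The documents support neither. An ordinary logistic fit has O/E of 1 in its own pooled data, so the realistic pooled concern is the slope, which is mildly to moderately below 1 in step 9.

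**Conclusion.** The point holds in a limited form. The plan names recalibration without any measure of calibration, and its trigger does not match the remedy. The invariance in step 1 depends only on how the cut-off is set, and step 2 only on recalibration meaning a change of intercept and slope. Both are firm.

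That the trigger can miss the site that needs recalibration, or flag one that does not, is shown only under the assumed shifts, with AUROC about 0.75 and no site term. Step 6 shows that the rule can also work. Calibration measures would add direction and separation from case mix; they would not add detection.

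The gap affects the recalibration step and any use of individual or graded risk. It does not undermine the classification aim. It should be corrected before analysis, but it is not a fatal flaw.

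**What to change.** In section 4.10:

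- For each model, add the optimism-corrected calibration intercept (or O/E), the calibration slope and a calibration plot, from the same resampling. Report calibration by site with 95% intervals.
- Where a method does not output a probability, such as a support vector machine score, map it to a risk inside the resampling.
- Base site recalibration, in either direction, on a calibration criterion set in advance. A direct test of the between-site difference in intercept is preferable: a logistic model with a site term and the model's linear predictor as offset. If a site O/E interval excluding 1 is used instead, state that it is conservative (about 39% / 64% detection at 1.5-fold odds).
- Treat a low site AUROC as a reason to check case mix or revise the model.
- Keep the five planned metrics and the sensitivity target above 80%.

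The cost is a few sentences and a little extra analysis on data already planned, with no added participants. The drawback is precision: site O/E intervals will be about 0.81 to 1.23 for mothers and 0.85 to 1.18 for newborns, so modest site differences will often stay uncertain.
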